**Appendix 2 Schedule of Clinical Laboratory Evaluations**

Observation	Screening	Total Kt/Vurea Visit
Blood Draw:		
Serum $\beta$ -hCG a	X	
Hepatitis B b	X	
Hepatitis C b	X	
CBC with differential	X	
Chemistry Profile c	X	
Creatinine d		X
Urea Nitrogen d		X
PD Effluent:		
White Cell Count with differential	X	
Cell Culture	X	
Total Kt/V urea d	X	X
24-hour PD Effluent Collection:		
Total Volume	X	X
Creatinine	X	X
Urea Nitrogen	X	X
24-hour Urine Collection:		
Total Volume	X	X
Creatinine	X	X

---

Observation	Screening	Total Kt/V urea Visit
Urea Nitrogen	X	X

a Women of childbearing potential (not menopausal or surgically sterile) must have a negative serum pregnancy test result within 14 days prior to initiation of study product.

-If qualitative serum  $\beta$ -hCG results are positive, repeat quantitative serum pregnancy test within 48 hours.

-If quantitative serum  $\beta$ -hCG levels show clinically significant rise, within 48 hours, serum progesterone level should be taken. Serum progesterone > 5 ng/mL will exclude a patient from the study.

b Patients will be screened (those without a history of positive Hepatitis B or Hepatitis C serology) for both infections at the Screening Visit.

-Hepatitis B: Hepatitis B surface antigen (HBsAg) in acute and chronic infection;

-Hepatitis C: Screening assay (EIA or CIA) for anti-Hepatitis C virus (HCV). Automatic verification of positive Screening results by an additional, more specific assay (e.g., nucleic acid testing [NAT] for HCV RNA).

c The chemistry profile includes glucose, calcium, albumin, total protein, sodium, potassium, bicarbonate, chloride, creatinine, blood urea nitrogen, alkaline phosphatase, alanine aminotransferase, aspartate amino transferase, bilirubin, and phosphorous.

d To assess total Kt/Vurea, 24-hour urine (if not anuric), 24-hour PD effluent, and serum will be collected at Screening. However, if a total Kt/Vurea is available from within 45 days of Screening, then it will be used as the Screening/Baseline value (i.e., no urine and peritoneal effluent samples will be collected to calculate Kt/Vurea). Total Kt/Vurea assessment will also occur after the patient has been dialyzing for at least 4 weeks with the AMIA APD Solution Generation System, (assessment done one time during Week 5, 6, 7 or 8 of the Study Treatment Period.)

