### **4.2 Inclusion Criteria**

Each patient must meet ALL of the following criteria to be enrolled in this study:

1. Patient is 18 years or older.
  2. Patient with ESRD receiving PD therapy, and who is already trained and regularly using the AMIA or HomeChoice APD Cycler with Dianeal PD Solution for at least 12 weeks.
- 
- 

- 
3. Patient is receiving or willing and able to use Dianeal Low Calcium (2.5 mEq/L) PD prescriptive regimen at study treatment initiation per Investigator's assessment.
  4. Patient demonstrates adequate PD therapy with clinical euvolemia as assessed by the Investigator with a total  $Kt/V_{urea}$  of a minimum of 1.7 within 45 days of Screening, or measured at Screening. If a total  $Kt/V_{urea}$  is not available within 45 days of Screening, it will be measured at Screening.
  5. Investigator assesses that, with appropriate training, the patient will be able to successfully manage his/her dialysis treatments with the AMIA APD Solution Generation System.
  6. Patient is available and is willing to complete training on the AMIA APD Solution Generation System.
  7. Patient and home environment are deemed suitable for treatment with the AMIA APD Solution Generation System, while in the home.
  8. Home electrical and water assessments meet suitability criteria for the AMIA APD Solution Generation System.
  9. The patient's home has suitable wireless connection or patient is willing to allow installation of suitable wireless connection.
  10. Patient and/or care partner (if participating) (See Section 5.4.1) is able to read and understand English, and provide informed consent after an explanation of the proposed study. If the patient does not read and understand English, patient may still participate if he/she has a co-residing care partner who reads and understands English, assessed as adequate by the PI.
  11. Women of childbearing potential (not menopausal or surgically sterile) must not be pregnant. Serum qualitative and quantitative pregnancy test will be done within 14 days prior to initiation of study product.
    - If qualitative serum  $\beta$ -hCG results are positive, repeat quantitative serum pregnancy test in 48 hours.
    - If quantitative serum  $\beta$ -hCG levels show clinically significant rise within 48 hours, serum progesterone level should be taken. Serum progesterone > 5 ng/mL will exclude a patient from the study.
- 
-

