#### **5.4 Selection and Timing for Each Patient**

Home suitability assessment and feed water testing will occur during the Screening Period. Home installation and product water testing are to occur during the Screening and/or the Baseline Period (In-center Training Period) to provide the most flexibility in patient's schedule. Patient will receive in-center training on the use of the system, which is to last approximately 2 weeks and is to begin after the Screening Period. Patient will continue to treat with standard AMIA or HomeChoice APD Cycler with Baxter's approved Dianeal Low Calcium (2.5 mEq/L) PD Solution during the Baseline Period (In-center Training Period). Baseline assessments are to occur during the Baseline Period (In-center Training Period) before the first treatment with the AMIA APD Solution Generation System. Patient will receive instructions on how to record his/her daily PD treatment and how to collect 24-hour peritoneal effluent and urine.

Following completion of the Baseline Period (In-center Training Period), the 12-week Study Treatment Period of in-home PD treatments using the AMIA APD Solution Generation System, will begin. The initial simulated treatment is to occur before the

patient administers his/her first PD treatment using AMIA APD Solution Generation System at home (Study Visit 1). Simulated treatments will continue during weeks 4 (Study Visit 2), 8 (Study Visit 3) and 12 (Study Visit 4) of the Study Treatment Period.

After the last treatment with the AMIA APD Solution Generation System, patient is to transition back to Standard AMIA or HomeChoice treatment with Baxter's approved Dianeal Low Calcium (2.5 mEq/L) PD Solution and enter a Follow-up Period of 5-10 days. Return of all investigational products and study related supplies will be scheduled during this time. The End-of-Study Visit is to occur on day 5-10 of the Follow-up Period.

The dialysis prescription for daytime exchanges should be kept consistent with the patient's pre-study prescription. The prescription of daytime dwells will not be modified unless determined to be clinically necessary by the Investigator. If a change in prescription occurs, it will be recorded in the patient's source data and accurately reflected in the eCRF.

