## **6.5 Clinical Laboratory Tests**

### **6.5.1 Laboratory Parameters**

Laboratory assessments will occur at Screening and after the patient has been dialyzing for at least 4 weeks (occurring one time during Week 5, 6, 7 or 8 of the Study Treatment Period), as outlined in [Appendix 2](#). If a patient misses 4 consecutive days of prescribed therapy with AMIA APD Solution Generation System then the total Kt/Vurea assessment (between Weeks 5-8) should be deferred by 1 week to allow a full week of prescribed treatment using the AMIA APD Solution Generation System.

---

Should a medical emergency arise, a local laboratory may be utilized; however, a copy of the laboratory certification, laboratory normal ranges and methodologies will be required. A list of laboratory tests is provided in [Table 4](#).

Because of the potential for false-positive beta serum human chorionic gonadotropin ( $\beta$ -hCG) test results in females with chronic kidney disease and end stage renal disease, both qualitative and quantitative serum pregnancy tests should be taken.

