## 8.2 Screening Period (approximately 3 weeks)

Consented patients who have met the study entry criteria will be allowed to continue their participation in the study and will undergo the Screening assessments and home evaluation.

The following procedures should be completed during the Screening Period:

1. Patients and care partners (if participating) (See Section 5.4.1) sign the ICF on the first day of the Screening Period.
  2. Record patient medical history (PD history including the APD prescription per day, history of peritonitis and other disorders or diagnosis). Medical history will also include demographics (age, gender, race, height, weight, body mass index calculated as weight (kg)/height (m), and ethnicity) and prior medications (all medications being taken at the time of Screening and 30 days prior to Screening, with each medication having a corresponding indication recorded on the Medical History eCRF form).
  3. Physical examination including weight and height.
  4. The date of the last total Kt/Vurea calculation should be noted (if a total Kt/Vurea is available from within 45 days of Screening, then it will be used as the Screening/Baseline value [i.e., no urine and peritoneal effluent samples will be collected for total Kt/Vurea]).
  5. Clinical laboratory evaluations as outlined in [Appendix 2](#).
  6. Vital signs including BP, pulse rate and temperature.
  7. Home suitability assessment.
  8. Feed water analysis for the home.
  9. Home Installation, when suitable.
  10. The PI or designee will assess each patient at the Screening visit and on a weekly basis, according to standard of care. At a minimum, this assessment will include evaluation of BP, pulse rate, weight, fluid status and dialysis prescription.
  11. Collection of concomitant medication information.
  12. Collection of AEs/ SAEs.
  13. The Investigator must assess the stability of the patient (Clinical and prescription stability).
-

14. If the patient is a screen failure, the reason for their failure must be recorded. Any patient who withdraws from the study before installation of the device is considered a screen failure. In addition, any patient who withdraws from the study after the installation but before confirming that all the inclusion criteria and none of the exclusion criteria are met, and withdraws due to a non-device related issue, is also considered a screen failure.

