### **8.4 Baseline Period (In-center Training Period)**

The Baseline Period (In-center Training Period) will begin immediately following the Screening Period, will include in-center training, and will last for approximately 2 weeks. The following information will be collected and procedures or evaluations will be performed:

1. Baseline Assessments
    - Assessment by an Investigator or a designee. At a minimum, this assessment will include evaluation of BP, pulse rate, weight, fluid status and dialysis prescription.
    - Collection of concomitant medication information.
    - Collection of AEs/ SAEs.
  2. Installation of the AMIA APD Solution Generation System in the patient's home (if not yet performed).
  3. AMIA APD Solution Generation System specific device training and general therapy training for the patient and care partner (if participating) (See Section [5.4.1](#)).
  4. Machine information including the available code number(s) and a lot/serial number(s) at initial installation and if the device or any of the disposables are changed.
- 
- 

5. Baseline Period (In-center Training Period) will conclude with:
  - Successful comprehension and retention testing, provided by Baxter, for the patient and/or care partner (if participating). If the patient does not read and understand English, the care partner will assist the patient with comprehension and retention testing.
  - The Investigator must reassess the stability of the patient during the Baseline Period (In-center Training Period). Once the clinician concludes that the patient is clinically stable and their PD prescription is stable, then the patient can begin treatment in the home.
  - Written confirmation of independent care by patient and care partner (if participating).

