l The Principal Investigator or a designee (e.g., sub-investigator) will assess each patient at the Screening Visit and on a weekly basis. At a minimum, this assessment will include evaluation of BP, pulse rate, weight, fluid status and dialysis prescription.

m AEs and SAEs will be collected after the informed consent is signed and will continue to be collected throughout the Study Treatment Period and during the follow-up period of 5-10 days after the last study treatment. Adverse device events and SADEs will be collected from the time of signing informed consent.

n Medications taken during the study will be documented throughout the study and will include a review of all major body systems and renal history (primary etiology of renal disease and current PD prescription).

o Patients will receive device-specific training which will last up to 2 weeks.

p Comprehension and retention testing will occur at the end of the Baseline Period (In-center Training Period) for patients and care partners (if participating). If the patient does not read and understand English, the care partner will assist the patient with comprehension and retention testing.

q The Investigator must reassess the stability of the patient during the Baseline Period (In-center Training Period). Once the clinician concludes that the patient is clinically stable and their PD prescription is stable, then the patient can begin treatment in the home.

r Written confirmation of independent care by patient and care partner (if participating).

s Machine information will include the available code number(s) and a lot/serial number(s) at initial installation and if the device or any of the disposables are changed.

t Machine observations with each treatment will include the following: duration of PD treatments, start and stop times, total UF volume programmed and removed as obtained from machine log, and technical treatment interruptions – machine alarms.

Observation	Screening (approx. 3 weeks)	Baseline Period (In-center Training, approx. 2 weeks) a	Simulated Treatment Visit 1 b	Each Treatment Day c	Treatment Visits 2, 3 and 4 (Treatment weeks 4, 8 and 12, respectively) d	Total Kt/V urea Visit e	Follow-up Period (5-10 days)	End of Study/ Early Termination Visit f

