y To provide schedule flexibility for the consented patient, Baxter Service or its designee may begin the home installation process during the Screening Period. System installation and product water from the WD (pre-sterilizing filters) testing are expected to take approximately two weeks. This will ensure the system is ready for activation after the patient completes their required training on the AMIA APD Solution Generation System.

z eDiary source data will include data not limited to treatment activities listed in section 5.9 of the protocol. If the patient does not speak English, the care partner will assist the patient with completion of the eDiary.

aa Feed water analysis for the home may take place at de-commissioning.

bb After the final Study Treatment Visit, patients are to transition back to treatments with AMIA or HomeChoice with Baxter’s approved Dianeal Low Calcium (2.5 mEq/L) PD Solution in their home environment and enter a 5-10 day Follow-up Period. Return of all investigational products and study related supplies will be scheduled during this time.

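### The serum pregnancy test must fall within 14 days before first study product, but it is scheduled only at Screening, ahead of a Baseline Period of about 2 weeks

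*Protocol*

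**What the plan says.** **The requirement.** Criterion 11 (Protocol Section 4.2, also in the Synopsis) states: "Serum qualitative and quantitative pregnancy test will be done within 14 days prior to initiation of study product". Appendix 2, footnote a, says that these women "must have a negative serum pregnancy test result within 14 days prior to initiation of study product". A positive qualitative result leads to a repeat quantitative test within 48 hours and, if the level rises, to serum progesterone.

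**The schedule.** Appendix 2 has two columns, Screening and the Total Kt/V visit, and marks serum beta-hCG under Screening only. Section 6.5.1 agrees: "Laboratory assessments will occur at Screening and after the patient has been dialyzing for at least 4 weeks", the latter meaning one occasion in Weeks 5 to 8. Appendix 1 of the Protocol, repeated as Appendix 1 of the SAP, marks clinical laboratory evaluations at the same two points. Neither the Baseline list in Section 8.4 nor the Study Visit 1 list in Section 8.6 contains a pregnancy test.

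**The calendar.** Section 8.2 gives Screening about 3 weeks. Section 8.4 says the Baseline Period "will begin immediately following the Screening Period, will include in-center training, and will last for approximately 2 weeks". During Baseline, under Section 5.4, "Patient will continue to treat with standard AMIA or HomeChoice APD Cycler" and approved Dianeal. Study treatment starts once Baseline is complete.

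**The concern.** The limit counts back from first use of study product, but the only scheduled test lies on the far side of a period about as long as the limit itself. A test done as scheduled will usually have expired by first treatment.

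Two things are at stake. A woman treated on an expired result has not met an inclusion criterion, and Section 9.2 rules out waivers for deviations. A pregnancy that begins between the Screening sample and first treatment would also meet no scheduled test. The conditions for leaving Baseline (Sections 6.9 and 8.4) are comprehension testing, clinical and prescription stability, and confirmed independent care. None asks about pregnancy or the age of the result.

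**Working it through.** **Are the periods sequential?** Section 3.4 gives total participation as about 18 weeks. Adding the parts: 3 + 2 + 12 weeks + 5 to 10 days = 17.7 to 18.4 weeks. This reproduces the stated figure, so Screening and Baseline run one after the other.

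**Inputs**
- Limit: 14 days before first study product (criterion 11; Appendix 2, footnote a).
- Screening: about 3 weeks, taken as 21 days (Sections 3.4 and 8.2).
- Baseline: about 2 weeks, nominally B = 14 days, directly after Screening (Section 8.4).
- Baseline of 10 or 7 days: assumed, to show the effect of a shorter period. Appendix 1, footnote o, allows some shortening: "Patients will receive device-specific training which will last up to 2 weeks".
- Simulated Treatment Visit 1: up to 7 days before first actual treatment (Appendix 1, footnote b).

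**Formula.** For a draw on Screening day s (1 to 21), sample age at first treatment is

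- (21 − s) + B, if treatment starts on the last Baseline day;
- (21 − s) + B + 1, if it starts the day after.

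Setting age ≤ 14 gives s ≥ 7 + B or s ≥ 8 + B. The number of complying draw days is therefore 15 − B or 14 − B.

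| Baseline B (days) | Sample age, treatment on last Baseline day | Sample age, treatment the day after | Complying draw days of 21 |
|---|---|---|---|
| 14 (nominal) | 14–34 | 15–35 | 1 or 0 |
| 10 (assumed) | 10–30 | 11–31 | 5 or 4 |
| 7 (assumed) | 7–27 | 8–28 | 8 or 7 |

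**Screening length.** The count of complying days depends on B and not on the length of Screening: a shorter or longer Screening Period leaves 15 − B or 14 − B complying days at its end, provided it has that many.

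**A first-day draw.** Its age is 20 + B or 21 + B: 34 to 35 days with B = 14, and 27 to 28 days with B = 7. It complies only if Screening and Baseline together last about 14 days, against a nominal 21 + 14 = 35.

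**Can Baseline be shortened?** Installation may fall within it, and Appendix 1, footnote y, says: "System installation and product water from the WD (pre-sterilizing filters) testing are expected to take approximately two weeks". Patients cannot treat at home until the post-installation water results have been reviewed (Sections 6.5.8.1 and 6.5.8.2). When installation waits until Baseline, a short Baseline is hard to achieve.

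**A lenient reading of initiation.** If Visit 1, held a full 7 days early, counted as initiation, each age would drop by 7 days. With B = 14 that is equivalent to B = 7: 7 to 8 of 21 days comply. The simulated treatment involves no patient exposure (Section 6.5.7), so this reading is generous, and most draw days still fail.

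**A test in Baseline.** On day d of a 14-day Baseline, age is 14 − d or 15 − d, that is 0 to 14 days. Every day complies. A draw at Visit 1 is 0 to 7 days old and also complies.

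**The case against.** The strongest reply is that the limit is not missing. It sits in the footnote to the very row that marks the test, and it is an entry criterion. Section 5.2 lets only patients who meet the criteria continue, so a careful site would draw late or repeat the test. Nothing prevents this: no text fixes the beta-hCG draw to the first Screening day, both periods are approximate, Sections 8.2 and 8.10 foresee eligibility being confirmed after installation, and Section 6.9 allows further tests under local standard of care. On this view the gap is one of clarity.

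The harm is also limited. The generated solution is nominally equivalent to Dianeal Low Calcium, and participants have used Dianeal for at least 12 weeks. Contraception is required, patients are assessed weekly, and pregnancy is a withdrawal reason with its own reporting procedure. Even a compliant 14-day-old result leaves some gap.

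Much of this stands. Compliance is possible, the longest ages are worst cases, and equal weight for each draw day is a convenience. But every route to compliance depends on a site noticing the conflict and acting outside the schedule. No scheduled step would catch an expired result. The similarity to Dianeal reduces the clinical consequence but does not alter the criterion.

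Objections to a Visit 1 draw also have force. Visit 1 takes place in the home, Section 8.6 lists no blood sample there, and time for a 48-hour repeat rules out the last days before treatment. This favours in-center training as the place for the draw.

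**Conclusion.** The concern holds. The schedule does not provide for a test that the protocol's own entry criterion requires. At nominal lengths a Screening sample is 14 to 35 days old at first treatment, and 0 to 1 of 21 draw days meets the limit. With an assumed 10-day Baseline 4 to 5 days comply, and with an assumed 7-day Baseline 7 to 8.

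These counts assume a 21-day Screening Period, Baseline directly after it, and first treatment on or just after the last Baseline day. A late draw followed by a short Baseline can comply, so a Screening-only test generally, but not always, misses the window.

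The point concerns eligibility and patient safety. It applies only to women of childbearing potential, whose number the documents do not give, and it leaves the primary endpoints and their analysis unchanged. It should be corrected.

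**What to change.** Keep the Screening test. Add a qualitative and quantitative serum beta-hCG late in the Baseline Period for any woman of childbearing potential whose Screening sample would be more than 14 days old at first treatment. In-center training is the easiest place to draw it; Simulated Treatment Visit 1 is an alternative.

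Draw it at least 48 hours before first treatment, plus laboratory turnaround, so that the repeat in footnote a can be completed. At Visit 1 this means a sample at least 2 and at most 7 days old. State that the result must be reviewed before first treatment, and add that check to the conditions for ending Baseline.

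The text to change is Protocol Sections 6.5.1 and 8.4, Appendices 1 and 2, and the copy of the schedule in SAP Appendix 1.

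The cost is one blood draw for the women concerned, and some constraint on the timing of Visit 1 if the draw is placed there. Table 4, footnote a, already has chemistry, serology and hematology done locally after Screening. It does not name beta-hCG, so the amendment should state which laboratory runs it.
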